## **Secondary Objectives**

- To assess the complications of treatment related to minimally invasive endoscopic skull base surgery in patients with unresectable disease using Clavien-Dindo classification of surgical complications
- To assess toxicity of treatment based on CTCAE v4.03 scores in the acute setting (throughout treatment and up to the 3 month visit after end of treatment)
- To assess toxicity of treatment based on CTCAE v4.03 scores in the long-term setting (after the 3 month post treatment visit until the 24 month post treatment visit)
- To assess toxicity of treatment related to patient reported outcomes including EORTC (H&N43 and C30) and Skull Base Inventory (SBI)
- To determine the 1- and 2-year rates of regional/nodal, or distant-metastasis progression incidence, progression-free survival, disease specific mortality, and overall survival in our group of patients undergoing NTR / proton-beam radiation therapy (PBRT) and chemotherapy
- To obtain tissue of these rare tumor types for IMPACT assessment. Results of IMPACT testing will be banked for future investigation

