### 10.1 Evaluation during concurrent chemo-proton radiotherapy treatment (please see Table 3 for details):

- Standard weekly treatment evaluations
- Weekly CTCAEv4 toxicity (Appendix 4) and adverse event assessment
- Clavien-Dindo Classification of Surgical Complications (Appendix 5)
- Patient completion of required patient reported outcome assessments including:
  - Study specific PRO instruments:
    - EORTC QLQ C30 & H&N 43
    - SBI

Table 3. ASSESSMENTS DURING PROTOCOL TREATMENT		
Assessments	Source	During Treatment
Toxicity and adverse events (CTCAEv4)	MD	Weekly throughout RT and at end of RT
Height and Weight	EMR	Postoperatively (pre RT), at week 4 of RT (+/- 7 days), and end of RT (+/- 7 days)
Postoperative MRI of the nasal cavity/paranasal sinuses	EMR	Should be completed 4 weeks post surgery (+/- 7 days)
History and Physical Exam	EMR	Safety evaluations during treatment with cisplatin involve weekly toxicity checks.
CBC and CMP	EMR	Safety evaluations during treatment with cisplatin involve weekly toxicity checks.
Clavien-Dindo Classification of Surgical Complication Assessment	MD	Postoperative but prior to radiation
EORTC QLQ C30 & H&N43	PSA	Postoperatively (pre RT), at week 4 of RT (+/- 7 days), and end of RT (+/- 7 days)
SBI	PSA	Postoperatively (pre RT), at week 4 of RT (+/- 7 days), and end of RT (+/- 7 days)

Abbreviations: MD (medical doctor); PSA (Patient self-administered with or without Research Study Assistant assistance); EMR (Electronic Medical Record)

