## **11.6 Adverse Event Reporting**

This study will use the Common Terminology Criteria for Adverse Events (CTCAE) version v4.03 for adverse event (AE) reporting. After the Informed Consent Document (ICD) is signed, study site personnel will record the occurrence and nature of each patient's pre-existing conditions, including clinically significant signs and symptoms of the disease. During the study, site personnel will record any change in the pre-existing condition(s), and the occurrence and nature of any new adverse events.

Expected events during radiation therapy are:

- Fatigue/malaise
- Weakness
- Nausea
- Mild anorexia
- Oral mucositis
- Radiation dermatitis
- Xerostomia
- Dysphagia
- Tinnitus
- Dysgeusia

General Therapy Related Events:

- Catheter related events (thrombosis, bleeding, infection)
- Hospitalization for the management of any of the above expected events

Reporting Results:

- All AEs related to protocol procedures are reported. All AEs occurring after the patient receives the first dose of radiation therapy must be reported in regard to their assessment of the potential relatedness of each AE to protocol procedure, studied disease state, and/or radiation modality via CRF. If a patient's radiation treatment is discontinued as a result of an AE, personnel must clearly report the circumstances and data leading to any such dosage reduction or discontinuation of treatment.
- Events leading to the clinical outcome of death due to disease progression will be included as part of the safety and efficacy analyses for this study.
- If a death is considered related to treatment, the death should be reported as a Serious Adverse Event and appropriate guidelines followed for SAE reporting. Any clinically significant findings from labs, vital sign measurements, and other procedures should be reported as well.

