### **14.0 BIOSTATISTICS**

A one-stage design will be used for this trial. Of the 25 patients to be enrolled, 15 will be SCC patients and the remaining 10 will be ACC, Esthesio, or Adenocarcinoma. Based on historical data, current standard non-surgical treatment has a 1-year local failure rate of 40% for SCC patients and 65% for ACC, Esthesio or Adenocarcinoma patients. Therefore, a mixed cohort of 15 SCC and 10 ACC/Esthesio/Adenocarcinoma patients should have 1-year local failure rate of 50% under standard non-surgical treatment. We expect to decrease such a rate to 25% using the proposed new treatment. This design depends on a one-arm, one-sided binomial test and has a decision rule as follows: If, among the total 25 patients enrolled, we have at least 17 patients who are alive, followed and local failure free (or equivalently, at most 8 patients who are dead, lost to follow up or withdrew from the study, or have local failure) one year from the end of the treatment, then we shall declare the proposed treatment strategy

worthy of further investigation. Any patient who is taken off study due to unacceptable toxicities or lost to follow up, dies or withdraws within one year from the end of treatment will be regarded as a local failure. Patients who die during treatment will also be counted as failures, though such a probability will be small. This design has a type 1 error rate of 0.05 and type 2 error rate of 0.15 for testing the hypothesis  $p \geq 50\%$  vs  $p < 25\%$ , where  $p$  represents the 1-year local failure rate.

To assess the complications of minimally invasive endoscopic skull base surgery in patients with unresectable disease, we will use Clavien-Dindo classification of surgical complications and summarize the grades (I-V) and types. This will be done after surgery but before radiation.

To assess acute and long-term toxicity of radiotherapy, we will summarize the CTCAE v4.03 scores and present descriptive statistics. This will be done weekly throughout RT, at the end of RT, and then 3 months after the end of RT for acute toxicities. Long-term toxicities will be assessed at 6, 12 and 24 months after the end of RT.

Patient reported outcomes of toxicity due to radiotherapy, EORTC (H&N43 and QLQ C30) and SBI, will be summarized and reported at the following time points: After surgery (pre RT), week 4 of RT (+/- 7 days), 1 week within end of RT, and then at 3, 6, 12 and 24 months after the end of RT.

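### The surgical-complication window closes when radiation starts and the CTCAE summary opens there under a radiotherapy label, so a surgical complication first seen later falls into the wrong summary

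*Combined protocol and SAP*

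**What the plan says.** **Surgical complications.** The first secondary objective is to describe complications of the endoscopic surgery with the Clavien-Dindo scale. Section 14.0 plans a summary of grades and types and adds "This will be done after surgery but before radiation". Table 3 gives the same timing: "Postoperative but prior to radiation". Table 4, the follow-up schedule, has no Clavien-Dindo row. The bulleted list in Section 10.1, under the heading for evaluation during concurrent chemo-proton radiotherapy, nevertheless includes "Clavien-Dindo Classification of Surgical Complications (Appendix 5".

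**CTCAE toxicity.** The acute-toxicity objective covers events "in the acute setting (throughout treatment and up to the 3 month visit after end of treatment". Section 4.3 defines the intervention as near-total resection followed by chemotherapy with proton radiation. Table 3 schedules CTCAE assessment as "Weekly throughout RT and at end of RT". Section 14.0 introduces the analysis with "To assess acute and long-term toxicity of radiotherapy, we will summarize the CTCAE v4.03 scores and present descriptive statistics" and gives the acute time points: "This will be done weekly throughout RT, at the end of RT, and then 3 months after the end of RT for acute toxicities". It plans no breakdown by attributed cause.

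**Relatedness.** Section 11.6 says "All AEs occurring after the patient receives the first dose of radiation therapy must be reported", and the same sentence asks that each such event be assessed on the CRF against protocol procedure, disease and radiation modality. Section 11.7.4 supplies four attribution categories for the research intervention as a whole.

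**The concern.** The two instruments meet at one calendar point, the start of radiation, and that point is not fixed relative to surgery. This has two consequences.

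First, time under observation for surgical harm varies. A patient who starts radiation early has a short surgical window and one who starts late has a long one. The background sections present an earlier start of adjuvant treatment as an advantage of endoscopic surgery, and under this rule the same feature shortens follow-up for surgical complications. For a patient who never starts radiation, the window has no stated end.

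Second, an event's summary is decided by its date and not by its cause. Resection in patients who might otherwise not have had surgery is one of the added elements under study, together with protons. In a single-arm trial the descriptive complication rate is the main evidence on surgical harm. If late surgical events drop out of it and enter a summary labelled as radiotherapy toxicity, both descriptions are distorted.

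**Working it through.** The point concerns assessment windows, and the plan states no figure to reproduce. The check sets the places side by side, follows an event through them, and then adds a calculation for scale.

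**1. Windows**

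| Place | Clavien-Dindo | CTCAE |
|---|---|---|
| Secondary Objectives | Own objective, no window | Acute: throughout treatment to the 3-month visit |
| 10.1 list | Listed under chemoradiation | Weekly |
| Table 3 | After surgery, before radiation | Weekly in RT and at end of RT |
| Table 4 | No row | 3, 6, 12 and 24 months |
| Section 14.0 | After surgery, before radiation | From RT onward, labelled radiotherapy toxicity |

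**2. Following a surgical complication by date of first appearance**

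- *Between surgery and radiation:* it enters the Clavien-Dindo summary. No CTCAE visit is scheduled and no CTCAE summary covers the interval, although the objective's wording, read with Section 4.3, can be taken to include it.
- *During radiation:* no Clavien-Dindo assessment is scheduled under Table 3 or Section 14.0. It is picked up at the weekly CTCAE assessment and enters the radiotherapy summary.
- *After radiation:* the same applies, through the Table 4 visits.

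**3. Length of the surgical window**

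Neither Table 3 nor Section 14.0 gives a number of days. The only dated assessment in the interval is the post-operative MRI, at 4 weeks +/- 7 days, that is, 3 to 5 weeks after surgery. It does not fix when radiation starts.

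**4. Scale**

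Inputs: n = 25 (Section 14.0); post-operative CSF leak rate 5% in published series and 3.2% at the centre (Section 11.1.1).

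- Expected leaks: 25 x 0.05 = 1.25; 25 x 0.032 = 0.80.
- Chance of at least one: 1 - 0.95^25 = 0.72; 1 - 0.968^25 = 0.56.
- One event moved between summaries: 1/25 = 4 percentage points. Exact (Clopper-Pearson) 95% intervals are 0 to 13.7% for 0/25 and 0.1 to 20.4% for 1/25.
- Let s be the share of leaks first seen after radiation starts. The documents do not give s, so it must be an assumption from 0 to 1. Expected leaks placed in the wrong summary are 1.25 x s, or 0 to 1.25, at the published rate, and 0.80 x s, or 0 to 0.80, at the centre's rate.

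These figures show how sensitive a 25-patient rate is to one event. They do not estimate a bias.

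**The case against.** The strongest case against is that the split between instruments is deliberate: the objectives give surgery its own scale and give CTCAE a separate role. Section 11.1.2 treats acute radiation effects as those from radiation to 3 months afterwards, which fits a CTCAE summary starting with RT. The phrase about treatment in the acute-toxicity objective need not be read as starting at surgery. The heading of Section 10.1 sends the reader to Table 3, which agrees with Section 14.0, so the bulleted list is a weak contradiction. All of this is fair. It explains why CTCAE starts with RT, but it still leaves a delayed surgical complication without a place in the surgical summary.

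A reader might infer two stronger conclusions that the documents do not support.

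- *That post-operative events carry no CTCAE grade.* Section 11.6 adopts CTCAE v4.03 for adverse event reporting, has new events recorded during the study and has events related to protocol procedures reported. Section 11.7.1 requires grade 3 or higher non-hematologic events to be graded. Section 11.8 has events tracked throughout the study. Section 17.3 requires SAE reports, with grade, from the start of the intervention. Only the scheduled assessment and the planned summary are missing before radiation.
- *That late surgical events will be attributed to protons in the data.* The Section 11.6 relatedness item, for events after the first radiation dose, distinguishes protocol procedure from radiation modality. Much of the information needed to separate them is therefore to be collected. The gap is that Section 14.0 does not use it.

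**Conclusion.** The point holds as a defect in the planned summaries. Followed as written, Section 14.0 and Table 3 leave a surgical complication first seen during or after radiation out of the surgical summary and place it in one labelled radiotherapy toxicity. The surgical rate also rests on an observation time that differs by patient. The Section 10.1 list and the acute-toxicity objective should be brought into line with whichever windows are chosen.

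The size is modest. One event is 4 points on a rate whose 95% interval at 1/25 already runs from 0.1 to 20.4%. It would be tempting to read the 5% and 3.2% leak rates as the size of the error, but they are overall rates, and no document says what share appears after radiation starts.

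The conclusion assumes that at least some surgical complications can first appear after radiation begins, and that the analysis follows the Section 14.0 time points. It affects descriptive secondary endpoints only; the primary decision rule is unaffected. This is an inexpensive improvement and not a condition for the trial's validity.

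**What to change.** 1. Summarise Clavien-Dindo over one pre-specified post-operative period, the same for every patient and independent of when radiation starts. Also grade any surgery-attributed event at the existing end-of-RT and 3-month visits.
2. Summarise CTCAE events from surgery onward, or from consent for patients operated on elsewhere, by attributed modality.
3. Extend the Section 11.6 CRF relatedness item to name surgery, chemotherapy and radiation, and apply it from the same starting point. The Section 11.7.4 categories alone cannot do this, because they attribute to the research intervention overall.
4. Make the Secondary Objectives, Section 10.1, Table 3, Section 11.6 and Section 14.0 state the same windows.

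The cost is one form at two existing visits, a small CRF change and protocol wording. There are two drawbacks: attributing an event that arises during radiation needs clinical judgement, and early events in patients operated on elsewhere must be retrieved from outside records, so they may be less complete.

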### **11.8 Follow-up of Adverse Events**

All adverse events will be followed up according to Good Clinical Practice.

During Treatment: Throughout the duration of the study, site personnel will track any change in the condition(s), the occurrence, and the nature of any AEs, and record the highest grade of the adverse event per cycle on the CRF. CTCAE grading will be assigned before each visit for any adverse events experienced during the previous visit period.

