### **13.1 CRITERIA FOR REMOVAL FROM STUDY**

If at any time the patient develops locally progressive disease, s/he will be taken off study and referred for alternative therapy. If at any time the patient develops unacceptable toxicity, s/he will be removed from the study. If at any time the patient dies while on study, s/he will be removed from the study. If grade 3 toxicity persists, requiring a break of more than five consecutive treatments, the participant will be taken off protocol therapy. We will, however, continue to follow them for the protocol.

The primary endpoint of which the power calculation is based on number of patients needed to observe a difference in local control following surgery then chemoradiation compared to historic rates of chemoradiation alone. Patients who are taken off study due to unacceptable toxicities will not be replaced as they will be counted as failures towards the primary endpoint. Patients who are lost to follow-up do not need to be replaced as they will be counted towards failures towards the primary endpoint. The chance of patients lost to follow-up (3 months from end of chemoradiation) is extremely low as all patients in our experience will return to see us for their first post-treatment follow-up visit. If at any time the patient is found to be ineligible for the protocol as designated in the section on Criteria for Patient/Subject Eligibility (i.e. a change in diagnosis), the patient will be reviewed and determined whether to keep on study or not at the discretion of the treating physician.

A patient has the right to withdraw from the study at any time for any reason without prejudice to his/her future medical care by the physician, or at the institution. Should a patient (or a patient's legally authorized representative) decide to withdraw, all efforts will be made to complete and report the observations as thoroughly as possible. A complete final evaluation should be made at the time of the patient's withdrawal. Patients will be removed from one or more parts of the study, at the Investigator's discretion, if one or more of the following events occur:

- Significant noncompliance on the part of the patient
- Refusal of the patient to continue treatment or observations
- Decision by the Investigator that termination is in the patient's best medical interest
- Patient is lost to follow-up 6 months post registration

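### Late toxicity and patient-reported outcomes are summarised only by visit, with no stated denominator, and Section 13.1 leaves unclear whether patients removed for toxicity or local progression are still assessed

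*Combined protocol and SAP*

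**What the plan says.** **Objectives (Section 2.1).** Late toxicity is a secondary objective defined as a window: after the 3-month post-treatment visit, up to the 24-month visit. Acute toxicity runs from treatment to the 3-month visit.

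**Analysis (Section 14.0).** For CTCAE, "we will summarize the CTCAE v4.03 scores and present descriptive statistics". The schedule for late effects is: "Long-term toxicities will be assessed at 6, 12 and 24 months after the end of RT". The EORTC and Skull Base Inventory scales are summarised at each listed time point. For these outputs the section names no analysis set, missing-data rule, worst-grade summary or cumulative figure.

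**Removal (Section 13.1).** "If at any time the patient develops unacceptable toxicity, s/he will be removed from the study". Patients with local progression also come off study and are referred elsewhere for treatment. Patients whose grade 3 toxicity forces a break of more than five treatments come off protocol therapy, and the next sentence promises continued follow-up.

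**Primary endpoint (Section 14.0).** Success is defined as "If, among the total 25 patients enrolled, we have at least 17 patients who are alive, followed and local failure free" at one year. Patients taken off study for toxicity within that year count as failures. No equivalent rule exists for toxicity or PRO outputs.

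**The concern.** A toxicity rate taken at a visit is sound only if leaving follow-up is unrelated to toxicity, or if those who leave are still counted. Here one stated reason for leaving is toxicity itself. If removal ends assessment, some of the most affected patients could be missing from the visits at which late effects are tabulated, and the remaining patients would look better than the treated group.

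The late window is a stated objective, yet no planned output says how many of the 25 treated patients had a severe late effect during it. For a strategy that adds surgery to chemoradiation, readers will want that number. Assessments that are never made cannot be recovered later.

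**Working it through.** **1. The plan's own figures.** The documents state no late toxicity rate, PRO value or expected loss to follow-up, so nothing on this point can be reproduced. The only checkable design figures are the error rates.
- Inputs (Section 14.0): 25 patients; at least 17 failure-free; null failure rate (15 × 0.40 + 10 × 0.65)/25 = 0.50; target failure rate 0.25.
- Exact binomial: P(X ≥ 17 | 25, 0.50) = 0.0539 and P(X ≥ 17 | 25, 0.75) = 0.8506, against a stated 0.05 and 0.85. The first agrees only when rounded to two decimals. Nothing below depends on it.

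**2. The Section 13.1 provisions side by side.**

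| Reason | Status given | Follow-up stated? |
|---|---|---|
| Unacceptable toxicity | off the study | not stated |
| Local progression | off the study | not stated |
| Persistent grade 3 toxicity with a long break | off protocol therapy | yes, in the next sentence |
| Patient's own withdrawal | withdrawn | best efforts to complete observations, plus a final evaluation |

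The follow-up sentence sits directly after the third row, and its scope for the first two is unclear. Radiation normally takes 7 weeks (Section 9.2.6). A patient removed for toxicity at month 6 or 12 has no protocol radiation or concurrent chemotherapy left to stop, so removal then would most naturally affect assessments.

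**3. How many might remain at 12 months.** Assume every primary-endpoint failure leaves assessment. At the 25% target rate, 25 × 0.75 = 18.75, about 19 patients. At the decision limit of 8 failures, 25 − 8 = 17.

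**4. Removal that depends on toxicity.** Assume 5 of 25 (20%) have a severe late effect that would still be present at the visit, and that k of them are removed first and not counted. The on-study rate is (5 − k)/(25 − k):
- k = 0: 5/25 = 20.0%
- k = 2: 3/23 = 13.0%
- k = 4: 1/21 = 4.8%

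The 20% and the values of k are assumptions; the documents give neither. If the removed patients' events were recorded at removal, a worst-grade summary over all treated patients returns 5/25 = 20% in every row.

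**5. Removal unrelated to toxicity.** Take 25% removed for local progression, independently of toxicity. Then 25 × 0.75 = 18.75 patients remain, of whom 0.20 × 18.75 = 3.75 are affected, and 3.75/18.75 = 20%. The rate is unbiased and only precision is lost.

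**6. What a visit figure leaves open.** If 19 are assessed and 2 are affected, the visit rate is 2/19 = 10.5%. Over all 25 it could lie anywhere from 2/25 = 8% to (2 + 6)/25 = 32%.

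**The case against.** The strongest reply is that the plan never says visit figures use only patients still on study, and never says removed patients stop being assessed. That is correct: both are inferences from silence. A reader might conclude that the worst-affected patients certainly disappear from the late figures. The documents do not support that, and four provisions weigh against it.

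- Section 11.6 requires adverse events after the first radiation dose to be reported on the case report form, and Section 11.7.1 requires non-haematologic grade 3 or higher events to be recorded. A severe event that triggers removal should therefore be captured.
- The follow-up sentence in Section 13.1 could be read more broadly than its position suggests.
- One- and two-year survival and disease-specific mortality imply some contact after local progression, though not CTCAE or PRO collection.
- Worst grade per window is not excluded by Section 14.0; it is just not specified.

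Two other strong readings also fail. Visit tables need not miss the cumulative proportion: Section 11.3 lists lasting effects, which remain visible at later visits if the patient stays in follow-up. And removal applies to local progression, not to any progression; by step 5 it does not bias the rate unless it is related to toxicity.

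What stands after this: capturing the triggering event on a form does not put it into a visit table, and nothing assures assessment after removal. Section 11.8 does say "CTCAE grading will be assigned before each visit for any adverse events experienced during the previous visit period", but under its during-treatment text, so it is weak support for late capture. Late grades depend on the Table 4 visits. Serious adverse event reporting narrows after 30 days to unexpected, possibly related events (Section 17.3).

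**Conclusion.** The point holds as a cheap improvement. Taken as written, the plan allows exit from late assessment to depend on toxicity, and provides no output that guards against it. The late toxicity figures can be selectively favourable; whether they will be depends on how Section 13.1 is applied and which denominator is used, and neither is stated. PRO summaries have the same undefined denominator.

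The size cannot be estimated from the documents. Under an assumed true rate of 20%, the visit figure could be anywhere from unaffected (20%) to 4.8% with four affected patients removed. This rests on removed patients being neither assessed nor counted. These are descriptive secondary outputs with no test attached, so the primary test, sample size and decision rule are not touched.

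**What to change.** 1. **Section 14.0, main toxicity output.** Over all treated patients, report the worst CTCAE grade per patient in the acute window (to the 3-month visit) and in the late window (after the 3-month visit to 24 months), counting events recorded up to and at removal. Optionally add the cumulative incidence of first grade 3 or higher late toxicity from the 3-month visit, with death as a competing event and with events after alternative therapy flagged.
2. **Section 14.0, visit tables.** Keep them as supportive. For CTCAE and PRO alike, show the number expected, the number assessed and the reasons for missing data at each visit.
3. **Section 13.1.** Reconcile the passages so that they say whether patients removed for toxicity or for local progression keep the scheduled CTCAE and PRO assessments to month 24 unless consent is withdrawn. No treatment-stopping rule needs to change.

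The cost is some wording in two sections and, if assessments continue after removal, a few extra visits. Reported toxicity may look higher than visit tables alone would show. Item 3 should be settled before any patient is removed.

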#### **4.3.1 Descriptions of PRO Instruments**

The PRO instruments and outcomes chosen for the proposed trials are well justified, hypothesis-driven, validated, reliable and meaningful to patients. Each instrument is described below. We estimate that patient response burden to complete these instruments will be approximately 35 minutes. The PRO instruments will be administered to patients preoperatively, at timepoints during the radiation and chemotherapy treatment period, and at post-treatment follow-up visits.

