## 8.0 PRETREATMENT EVALUATION

All patients will receive the necessary scans and tests according to the standard of care for their paranasal/nasal cavity malignancy.

Table 2 contains all the tests that will be performed within 8 weeks of the start of surgery and then chemoradiation.

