**Table 2: PRE-TREATMENT ASSESSMENTS**

[figure not shown]
Assessments	Source	Prior to protocol calendar days
Consent form signed by patient	CRC	1-3 weeks A
History B	EMR	30 days

Physical	EMR	30 days
Audiogram	EMR	6 weeks
CBC, CMP, Hepatitis B Core and Surface antigen	EMR	6 weeks
Dental Evaluation	EMR	6 weeks
Pregnancy test C	EMR	14 days prior to surgery
Karnofsky performance status	EMR	6 weeks
PET-CT with CT Neck component to include IV contrast and MRI of the Nasal Cavity/Para-Nasal Sinuses with contrast D	EMR	4 weeks
SBI	PSA	6 weeks
EORTC QLQ C30 & H&N 43	PSA	6 weeks

A: Patients start treatment within 30 days from time of consent as per institution's standard  
 B: For cisplatin eligibility requirement, a medical history for neuropathy, history of kidney disease, diabetes, hypertension, and cardiac disease.  
 C: For women of childbearing potential: Pregnancy testing should be performed according to institutional standards.  
 D: Patients with contrast allergies should be pre-medicated; patients with specific contrast contraindications can have contrast administration deferred.  
 Abbreviations: CRC (Clinical Research Coordinator);PSA (Patient self-administered with or without CRCAssistance); EMR (Electronic Medical Record)

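### Section 14 leaves the pre-operative questionnaires out of the patient-reported outcome summary, so the planned output cannot show change across the resection, for better or worse

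*Combined protocol and SAP*

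**What the plan says.** Collection. Section 4.3.1 states: "The PRO instruments will be administered to patients preoperatively, at timepoints during the radiation and chemotherapy treatment period", and again at follow-up visits. Section 8.0 introduces the pre-treatment table with "Table 2 contains all the tests that will be performed within 8 weeks of the start of surgery and then chemoradiation". That table has a row for the SBI and a row for "EORTC QLQ C30 & H&N 43", each with a 6-week window. Table 3 in Section 10.1 repeats the questionnaires "Postoperatively (pre RT), at week 4 of RT (+/- 7 days), and end of RT (+/- 7 days"), and Table 4 in Section 10.2 repeats them at 3, 6, 12 and 24 months.

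Analysis. Section 14.0 names the time points to be summarised. The first three are "After surgery (pre RT), week 4 of RT (+/- 7 days), 1 week within end of RT"; the other four are the Table 4 visits. The sentence that carries this list describes the outcomes as reflecting the toxicity of radiotherapy. The paragraphs that follow define the subscales and say that they are summarised at each time point. They define no baseline and no change score.

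Objective. The matching secondary objective reads "To assess toxicity of treatment related to patient reported outcomes including EORTC (H&N43 and C30) and Skull Base Inventory (SBI"). It refers to treatment and is not limited to radiotherapy. Section 4.3 defines the intervention as near-total endoscopic resection followed by cisplatin-based chemotherapy with proton radiation.

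**The concern.** Near-total resection is one of the components that this trial adds to non-surgical care. Section 3.6 expects the combined approach to limit toxicity and describes endoscopic resection as carrying little morbidity. A reader will look to the patient-reported outcomes to see whether patients agree. A post-operative level cannot answer that without the level before surgery.

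The instruments suit the question. Section 11.1.1 expects crusting, congestion and altered smell and taste after the operation. The H&N43 senses scale and the SBI nasal domain cover that ground, and Section 4.3.3.2 reports that the SBI was validated in patients having skull base surgery.

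A second, smaller matter is that levels reported visit by visit come from different sets of patients as follow-up proceeds. A shift between two visits may be change within patients, loss of the sicker patients, or both.

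**Working it through.** The plan states no figure on this point, so there is none to reproduce. The check sets the collection schedule beside the analysis list.

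**1. Time points**

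| Assessment | Collected | Summarised in Section 14.0 |
|---|---|---|
| Pre-operative | Yes (4.3.1, Table 2) | **No** |
| Post-operative, before RT | Yes (Table 3) | Yes |
| Week 4 of RT | Yes (Table 3) | Yes |
| End of RT | Yes (Table 3) | Yes |
| 3 months | Yes (Table 4) | Yes |
| 6 months | Yes (Table 4) | Yes |
| 12 months | Yes (Table 4) | Yes |
| 24 months | Yes (Table 4) | Yes |

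Collected: 1 + 3 + 4 = 8. Summarised: 3 + 4 = 7. No other section plans a summary of the pre-operative value.

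**2. Scores affected**

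From Section 14.0: 15 (C30) + 19 (H&N43) + 11 (SBI domains) + 1 (SBI composite) = 46.

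**3. Scope**

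The objective covers treatment; Section 14.0 covers radiotherapy. The treatment includes the resection, so the analysis is narrower than the objective by exactly that component.

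**4. Changing set of patients**

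Section 13.1 takes patients with local progression off study. At the hoped-for 1-year failure rate, 25 × 0.25 = 6.25, so about 6 of 25 patients would be failures by 12 months. At the historical rate, 25 × 0.50 = 12.5. Under the plan's rule these counts include deaths, withdrawals and losses to follow-up. The documents do not say whether questionnaires continue after removal for progression. If they stop, the 12-month summary could rest on roughly 12 to 19 patients. This is an illustration, since the documents give no completion rate.

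**5. What a paired change could show**

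The half-width of a 95% interval for a mean within-patient change, in units of the SD of that change, is t(0.975, n − 1)/√n.

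| Patients with both values | Half-width |
|---|---|
| 25 (all) | 0.41 SD |
| 20 (assumed) | 0.47 SD |
| 15 (assumed) | 0.55 SD |

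This is enough for a useful description, but not for firm inference on many scales.

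**The case against.** The strongest reply is that Section 14.0 says what its patient-reported summary is for, namely radiotherapy toxicity, and for that purpose the assessment between surgery and radiotherapy is the natural reference. Surgical morbidity has its own secondary objective and its own summary, the Clavien-Dindo grades. The outcomes are secondary and descriptive, and because the pre-operative data will exist, the change can be computed later.

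Part of this stands. The post-operative value should stay as the reference for radiotherapy effects, and no data are lost. It does not close the gap. The patient-reported objective is worded for treatment as a whole. Clavien-Dindo is graded by the physician, and Section 3.5 itself argues that patient reports add to clinician assessment. Section 14.0 is an explicit list, and with 46 scores a reference chosen after the data are seen invites selective reporting.

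It is also fair to object to an oversized remedy. Change with an interval for every score at every later visit would give 46 × 7 = 322 intervals in at most 25 patients. If nothing had changed, about 322 × 0.05 ≈ 16 would exclude zero by chance. The gap does not require that.

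Some stronger readings are tempting but unsupported:

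- **Surgery lowers the scores, so the omission hides harm.** The background on nasal cavity and paranasal sinus tumors says that debulking can relieve symptoms from tumour bulk. The omission could equally hide benefit, and in a single arm the change would combine the two.
- **The first reported questionnaire comes about 4 weeks after surgery.** In Table 3 that timing belongs to the post-operative MRI. The questionnaire rows give no week.
- **Pairing yields a particular gain in precision.** The documents give no correlation between visits, and the plan proposes no unpaired comparison of visits against which to measure a gain.
- **Patients operated on elsewhere have no pre-operative questionnaire.** Sections 6.2 and 9.1 allow their enrolment but say nothing about their questionnaires. They may lack one.

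**Conclusion.** The point holds as a mismatch between the analysis plan and a stated secondary objective. One of eight scheduled assessments is missing from the list, for all 46 scores, and it is the only one from which change across surgery can be measured. Following Section 14.0 as written leaves the patient-reported objective unanswered for the resection.

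This conclusion rests on the text alone. It needs no assumption about the direction of the surgical effect, correlation between visits or completion rates. The counts of patients and pairs in the check are illustrations only.

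The consequence is limited. The omission concerns the planned output and not data collection. It is a correction worth making before analysis, and no flaw in the main design.

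**What to change.** In Section 14.0:

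1. Add the pre-operative assessment to the list of patient-reported time points.
2. Word the analysis for toxicity of treatment, to agree with the secondary objective.
3. Report descriptively the within-patient change from the pre-operative to the post-operative (pre-RT) value for each score, with the number of patients who have both values. For later visits, report change from the pre-operative value for a short set of scales named in advance.
4. Keep the post-operative (pre-RT) value as the reference for statements about radiotherapy.
5. State separately how many patients operated on elsewhere have no pre-operative questionnaire.

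Paired change keeps the same patients on both sides of each comparison. It does not make those still answering at 24 months representative of all who enrolled, so the number with both values should appear at each visit.

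The cost is a wording change and additional descriptive tables. There is no multiplicity control over many scales, and the report should say so.
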